## 3.2.5. Solicited symptoms

This analysis will be performed for Month 2 only.

The number and percentage of subjects reporting each individual solicited local and general AE during the solicited follow-up period will be tabulated with exact 95% CI.

The number and percentage of vaccine injections followed by each individual solicited local and general AE will be tabulated, overall vaccination course, with exact 95% CI.

| gsk
GlaxoSmithKline | Stu                | dy RAP           |
|------------------------|--------------------|------------------|
| Study Id: 108706       | Abbreviated Title: | PRO HIV-005      |
| Version: Draft version | ⊠ Final            | Date: 26SEP 2008 |

The maximum intensity of fever and local injection site redness/swelling will be scored as follows:

| Symptoms                       | Grade | Scale             |
|--------------------------------|-------|-------------------|
| Fever                          | 0     | ] 37.5°C          |
| (Oral or Axillary temperature) | 1     | [ 37.5°C – 38°C ] |
| . ,                            | 2     | ] 38°C – 39°C ]   |
|                                | 3     | [ 39°C            |
| Redness/Swelling               | 0     | 0 mmm             |
|                                | 1     | [ 20 mm           |
|                                | 2     | ]20 mm – 50 mm ]  |
|                                | 3     | ] 50 mm           |

The same tabulations will be done for grade 3 adverse events and/or for adverse events with relationship to vaccination.

The number and percentage of of subjects reporting a solicited symptom will be also presented by duration ( $\leq 2$  days or > 2 days).

For fever, temperatures will be also summarized in 0.5°C increments.

The number of days with a solicited symptom during the solicited follow-up period will be aslo presented. The same tabulations will be done for grade 3 adverse events and/or for adverse events with relationship to vaccination.

## 3.2.6. Unsolicited symptoms

This analysis will be performed for Month 2 only.

The proportion of subjects with at least one report of unsolicited AE classified by the Medical Dictionary for Regulatory Activities (MedDRA) and reported up to 30 days after vaccination will be tabulated with exact 95% CI.

The same tabulations will be done for grade 3 adverse events and/or for adverse events with relationship to vaccination.

#### 3.2.7. Serious adverse events

Serious AEs and withdrawal due to AEs will be described in detail for both the Month 2 and thre Month 12 analyses.

| gsk
GlaxoSmithKline | Study RAP          |                  |
|------------------------|--------------------|------------------|
| Study Id: 108706       | Abbreviated Title: | PRO HIV-005      |
| Version: Draft version | n 🛛 Final          | Date: 26SEP 2008 |

### 3.2.8. Haematological and biochemical parameters

The frequency distribution of values below, within and above normal ranges will be tabulated per treatment group at each scheduled time point. In addition, change from baseline will be also tabulated.

Cleaning for these data for the month 12 analysis will only performed in a second step. This has no impact on the other analyses to be performed, as these data will not impact on the cohort definition.

### 3.2.9. Concomitant medication

This analysis will be performed for Month 2 only.

The number and percentage of subjects with concomitant medication(s), with antipyretics, with antibiotics and with immunosuppressant within 30 days post-vaccination will be tabulated with exact 95% CI. Concomitant medications will be classified in antipyretics, antibiotics and immunosuppressant according to the WHO drug dictionary.

### 3.2.10. Exploratory analyses

Analyses of solicited symptoms will be also performed with the following grading to facilitate comparisons with other GSK studies:

| Symptoms                       | Grade | Scale                |
|--------------------------------|-------|----------------------|
| Fever                          | 0     | ] 38°C               |
| (Oral or Axillary temperature) | 1     | [ 38°C – 38.5°C [    |
| ,                              | 2     | [ 38.5°C – 39°C [    |
|                                | 3     | [ 39°C – 40°C [      |
|                                | 4     | [40°C                |
| Redness/Swelling               | 0     | ≤ 20 <del>0</del> mm |
|                                |       | (amendment 1)        |
|                                | 1     | ]20 mm – 50 mm]      |
|                                | 2     | ]50 mm – 100 mm ]    |
|                                | 3     | ] 100 mm             |

| gsk
GlaxoSmithKline | Stu                | dy RAP           |
|------------------------|--------------------|------------------|
| Study Id: 108706       | Abbreviated Title: | PRO HIV-005      |
| Version: Draft version | ⊠ Final            | Date: 26SEP 2008 |

## 3.3. Immunogenicity

### 3.3.1. Cohorts and stratification

The primary analysis will be based on the ATP cohort for analysis of immunogenicity. If the percent of enrolled subjects excluded from this ATP cohort is more than 5%, a second analysis based on the Total Vaccinated cohort will be performed to complement the ATP analysis.

It has been decided to present the results for Month 6 and Month 12 based on the Month 12 cohort definition, while all results produced at Month 2 analysis will be based on Month 2 cohort. For clarity purposes, Month 12 analyses which include only descriptive summaries will be presented in separate tables with only the relevant time points included (Month 6 and Month 12).

### 3.3.2. Derived and transformed data

#### Serology data

- The cut-off values for antibody titers will be defined by the laboratory before the analysis.
- A seronegative subject is a subject whose titer is below the cut-off value.
- A seropositive subject is a subject whose titer is greater than or equal to the cut-off value.
- The seropositivity rate is defined as the percentage of seropositive subjects.
- The Geometric Mean Titers (GMTs) calculations will be performed by taking the anti-log of the mean of the log titer transformations. Antibody titers below the cut-off of the assay will be given an arbitrary value of half the cut-off for the purpose of GMT calculation.

#### ICS data

- ICS data will be expressed as antigen-specific CD4+/CD8+ T-cells per million respectively of CD4+ or CD8+ T-cells.
- The cut-off will be choosen on the basis of pre-vaccination response for all subjects, by examining percentiles (95th percentile included) of the different antigens and the different cytokines (amendment 1). A 95th percentile will be determined for each antigen on the CD4 expressing at least two cytokines (all doubles) for CD4 responses and on the CD8 expressing at least one cytokine for CD8 responses.

| gsk
GlaxoSmithKline | Stu                | dy RAP           |
|------------------------|--------------------|------------------|
| Study Id: 108706       | Abbreviated Title: | PRO HIV-005      |
| Version: Draft version | ⊠ Final            | Date: 26SEP 2008 |

# The cut-off will be defined as the rounded (superior hundred) maximum 95th percentile among the 4 antigens (amendment 1).

- A responder is a subject with antigen-specific CD4+/CD8+ T-cells response greater than or equal to the cut-off value.
- Frequency of CD4+/CD8+ T-cells expressing cytokines to the fusion protein F4co (all antigens) will be estimated by adding individual frequencies of CD4+/CD8+ T-cells to each 4 antigens (p17, p24, Nef, RT).

| gsk
GlaxoSmithKline   | Stu                | ıdy RAP          |
|--------------------------|--------------------|------------------|
| Study Id: 108706         | Abbreviated Title: | PRO HIV-005      |
| Version: 🗌 Draft version | on 🛛 Final         | Date: 26SEP 2008 |

### 3.3.3. Lab assays for immunogenicity

The following table describes the lab assays that will be analyzed for immune response:

| Assay   | Assay
method           | Test kit/
Manufacturer | Assay unit  | Assay
cut-off or
Limit of
detection | Laboratory         |
|---|---------------------------|---------------------------|---|--|--------------------|
| Anti-p17,-24,-RT,-
Nef, -F4co antibodies       | ELISA                     | In-house ELISA            | EU/mL   | To be
determined                          | CEVAC,
Belgium  |
| p17-,24-,RT-,Nef-
specific effector
T-cells | Flow
Cytometry,
ICS | In-house ICS              | Number of
cytokine(s)
positive cells
per 10  cells | To be
determined                          | *CEVAC,
Belgium |

\* Or GSK Biologicals,

## 3.3.4. Handling of missing data

For a given subject and a given immunogenicity measurement, missing or non-evaluable measurements will not be replaced.

For the calculation of percentage of responders to 1, 2, 3 and all 4 antigens, subjects with missing data to at least one of the concerned antigen(s) will not be taken into account.

## 3.3.5. Cell-mediated immune response

#### 3.3.5.1. Within group assessment

#### CD4+ and CD8+ T-cells response

For cell-mediated immune response, the following parameters will be tabulated by vaccine groups at months 0, 2, 6, 12 and at day 44 (two weeks after the second vaccination):

- descriptive statistics of the frequency of CD4+/CD8+-T cell expressing at least two different cytokines (IFN-γ, IL-2, TNF-α,CD40L) to each antigen and to all antigens;
- descriptive statistics of the frequency of CD4+/CD8+ T cell expressing at least IFN-γ and another cytokine (IL-2, TNF-α,CD40L) to each antigen and to all antigens;
- descriptive statistics of the frequency of CD4+/CD8+-T cell expressing at least IL-2 and another cytokine (IFN-γ, TNF-α, CD40L) to each antigen and to all antigens;
- descriptive statistics of the frequency of CD4+/CD8+-T cell expressing at least TNFα and another cytokine (IFN-γ, IL-2,CD40L) to each antigen and to all antigens;
- descriptive statistics of the frequency of CD4+ T cell expressing at least CD40L and another cytokine (IFN- $\gamma$ , IL-2, TNF- $\alpha$ ) to each antigen and to all antigens.

| gsk
GlaxoSmithKline | Stu                | dy RAP           |
|------------------------|--------------------|------------------|
| Study Id: 108706       | Abbreviated Title: | PRO HIV-005      |
| Version: Draft version | n 🛛 Final          | Date: 26SEP 2008 |

#### CD4+ T-cells expressing IL-2 and another cytokine

For CD4+ T-cells expressing IL-2 and another cytokine response, the following parameters will be tabulated by vaccine groups at months 0, 2, 6, 12 and at day 44 (two weeks after the second vaccination):

- percentage of responders to each antigen (p17, p24, Nef, RT);
- percentage of responders to at least one antigen (p17, p24, Nef or RT);
- percentage of responders to at least two antigens;
- percentage of responders to at least three antigens;
- percentage of responders to all four antigens (p17, p24, Nef and RT).

In addition, percentage of responders to one, two, three and four antigens will be tabulated, with and without specification of antigens.

**CD8+** *T***-cells expressing at least 2 cytokines (H**-2 and/or TNF-α and/or IFN-γ and/or-**CD40-L**) (amendment 1)

For CD8+ T-cells, the following parameters will be tabulated by vaccine groups at months 0, 2, 6, 12 and at day 44 (two weeks after the second vaccination):

- descriptive statistics of the frequency of CD8+ T cell expressing at least one cytokine (IFN-γ and/or TNF-α) to each antigen and to all antigens
- descriptive statistics of the frequency of CD8+ T cell expressing only TNF-α to each antigen and to all antigens
- descriptive statistics of the frequency of CD8+ T cell expressing only IFN-γ to each antigen and to all antigens
- descriptive statistics of the frequency of CD8+ T cell expressing IFN-γ and TNFα to each antigen and to all antigens
- for CD8+ T-cells expressing at least one cytokine, percentage of responders to each antigen (p17, p24, Nef, RT) (amendment 1)

#### 3.3.5.2. Between group assessment

For the following analyses, statistically significant differences (p-value  $\leq 0.05$ ) should be interpreted with caution as adjustment for multiplicity of endpoints and clinical relevance of the difference will not considered.

| gsk
GlaxoSmithKline | Stu                | dy RAP           |
|------------------------|--------------------|------------------|
| Study Id: 108706       | Abbreviated Title: | PRO HIV-005      |
| Version: Draft version | 🗵 Final            | Date: 26SEP 2008 |

### Analysis of frequency of CD4+ T-cells

A two-way ANOVA test will be performed on frequency of CD4+ T-cells expressing at least IL-2 to compare three doses of antigen F4Co with or without adjuvant two weeks after the second vaccination. The ANOVA model will include the doses (10  $\mu$ g, 30  $\mu$ g and 90  $\mu$ g) and the "adjuvants" (AS01B and WFI) as fixed effects.

If requires, the analysis will be performed on log10 frequency of CD4+ T-cells.

If interaction between doses and "adjuvant" is significant (p-value  $\leq 0.05$ ), comparison of doses will be done by "adjuvant" factor.

If difference between the three doses is significant (p-value  $\leq 0.05$ ), multiple comparisons will be performed and relationship between doses and CD4+ T-cell response will be also assessed.

ANOVA analyses will be done for each antigen (p17, p24, RT, Nef) and for the fusion protein F4Co.

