- Vaccination process: A staggered dose-escalation design will be used for safety • reasons. A first group of 12 subjects (10 receiving the adjuvanted vaccine and 2 receiving the vaccine in WFI) will be enrolled to receive their first vaccination at the lowest dose (10 µg), at a rate of maximum 1 subject per day during the first 5 working days. Provided no safety issues leading to clinical hold or stop occurred (Figure 2), the 12 subjects will be allowed to receive their second vaccination on Day 30, according to the same rate (1 subject/day during the first 5 working days). The remaining subjects of the same dose group (N=48) will receive their first vaccination. Then, a new group of 12 subjects will be enrolled to receive their first vaccination at the medium dose (30 µg) at a rate of maximum 1 subject per day during the first 5 working days. Provided no safety issues leading to clinical hold or stop occurred, subjects will be allowed to receive their second vaccination on Day 30 at the same rate, the remaining subjects (N=48) of the same dose group will receive their first vaccination. Then, a new group of 12 subjects will be enrolled to receive their first vaccination at the highest dose (90 µg) at a rate of maximum 1 subject per day during the first 5 working days. Provided no safety issues leading to clinical hold or stop occurred, subjects will be allowed to receive their second vaccination on Day 30 at the rate of maximum 1 subject per day during the first 5 working days and the remaining subjects (N=48) of the same dose group will receive their first vaccination. Exactly the same methodological approach will be replicated for the

third vaccination in each dose group (see Section 5.6.3).(Amended September 24, 2007)

- Blinding: Partially blind: observer-blind for adjuvantation, open for antigen content
- Treatment allocation: Randomized for the adjuvantation (AS01B or water for injection) (see Section 6.4 for a detailed description of the randomization method).
- Three *Two*-vaccination course given at 0, *and* 1 and 6-months. All vaccinations will be administered by the intramuscular route in the deltoid of the non-dominant arm. (Amended September 24, 2007)
- Duration of the study: The intended duration per subject will be approximately 14 months
- 7-day follow-up visits after each vaccination for the 12 first vaccinated subjects and 30-day follow-up visits after each vaccination for all subjects.
- Blood samples will be collected at 8 visits

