6.4.2. Randomization of subjects

The treatment allocation at the investigator site will be performed using a central randomization system on Internet (SBIR). The randomization algorithm will use a minimization procedure accounting for centre and vaccine dose (10, 30 or 90 μ g). Center and dose minimization factors will have equal weight in the minimization algorithm.

After having checked that a subject is eligible, and after informed consent has been obtained, the person in charge of the vaccination will access the randomization system on Internet to receive a treatment number. Upon providing a subject number and a vaccine dose (10, 30 or 90 μ g), the randomization system will use the minimization algorithm to determine the treatment number to be used for the subject.

The actual treatment number used for the first vaccination of the subject must be recorded by the investigator in the eCRF (Rando/Treatment Allocation Section).

When the first target number of 12 subjects has been reached for a given dose (10, 30 or 90 μ g), the enrolment will be frozen for the safety evaluation. When a go decision has been taken, the enrolment will be re-opened for that dose until the total target number of 60 subjects has been reached.

The enrolment for each vaccine dose (adjuvanted or not) will be open in a staggered way. The enrolment for 30 μ g vaccine dose will be open after completion of enrolment for 10 μ g vaccine dose and the enrolment for 90 μ g vaccine dose will be open after completion of enrolment for 30 μ g vaccine dose.

[figure not shown]

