Appendix C Overview of the Recruitment Plan

The investigator may use one of the following strategies for recruiting volunteers:

- Advertising / posters inside Ghent University Hospital buildings
- Group meetings
- University and Hospital personnel and students
- E-mails to the existing volunteers
- Recruitment via the center's website http://www.cevac.be
- If needed: advertisement (via an interview with an investigator) in the regional/Flemish written and spoken media.

At the study center, subjects will be screened for admission criteria and the first 180 subjects who meet all inclusion/exclusion criteria will be enrolled and allocated a randomization number according to the order in which they are enrolled.

The enrollment period, i.e., the period between the study start and the last enrolled subject, is maximum 20 weeks. This will be followed by the study monitor.

The recruitment plan must be discussed and defined with the Investigator by the Site Monitor.

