Collect blood by venipuncture in Terumo tubes with heparin (or equivalent) and record time of collection. The tubes should be kept at room temperature and shipped to a designated clinical site for separation of peripheral blood mononuclear cells (PBMCs). The shipment must be timed to ensure that PBMC separation will be performed within 24 hours. Use well closed styrofoam boxes of 5 cm thickness for blood samples transport (see current version of GSK Biologicals SOP RD_HCI_001 for guidance).

2. Separation and freezing of PBMCs

PBMCs will be separated on a density gradient, aliquoted and frozen at --80°C for 24 hours and further cryopreserved in liquid nitrogen until testing (see GSK Biologicals SOP: RD_HCI_007 for guidance).

- 3. Labelling of cryotubes for PBMC samples
- If labels are provided by GSK, it is mandatory to use them.
- If necessary, any hand-written additions to the labels should be made using indelible ink.
- 4. Sorting and storage of PBMC samples

Samples should be stored in liquid nitrogen until shipment to GSK Biologicals, if needed. Wherever possible, a backup facility for storage of samples should be available.

A standard Cryotube Listing Form (see current version of GSK Biologicals SOP RD_HCI_009 for guidance) specifying the samples being shipped for individual subjects at each timepoint, should be prepared for each shipment. A copy of this list should be retained at the study site, while the original should be sealed in a plastic envelope and shipped with the PBMC samples.

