## 2.2.2. Secondary endpoints

- Frequency of p17, p24, Nef and RT-specific CD4+ T cells expressing IL-2 and/or TNF-α and/or IFN-γ and/or CD40-L, as determined by ICS at Months 0, 2, 6, 12 and at Day 44 (two weeks after the second vaccination).
- Frequency of p17, p24, Nef and RT-specific CD4+ T cells expressing at least 2 cytokines including IL-2 equal or above the cut-off at Months 0, 2, 6, 12 and at Day 44 (two weeks after the second vaccination).
- Antibody titers to p17, p24, Nef, RT and F4co as measured by ELISA at Months 0, 2, 6, 12 and at Day 44 (two weeks after the second vaccination).

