## Analysis of responders in terms of CD4+ T-cells

A logistic regression will be performed on occurrence of responders in terms of CD4+ Tcells expressing at least IL-2 (dichotomous response, 0 or 1) to compare three doses of antigen F4Co with or without adjuvant two weeks after the second vaccination. Doses, "adjuvant" and interaction will be included in the logistic model.

If interaction between doses and "adjuvant" is significant (p-value  $\leq 0.05$ ), a logistic regression will be applied by "adjuvant" factor.

Logisitic regressions will be done for responders to at least one, two, three and 4 antigens (p17, p24, RT or/and Nef).

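### The Day 44 dose comparisons are between non-randomised cohorts enrolled in sequence, and the models leave out each subject's Day 0 ICS value, which would be a cheap partial safeguard

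*SAP*

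**What the plan says.** **Allocation.** The design overview (Protocol 3) gives "Treatment allocation: Randomized for the adjuvantation (AS01B or water for injection") and names no randomisation of dose. Protocol 6.4.2 has the site supply the dose to the system: "Upon providing a subject number and a vaccine dose", a treatment number is returned. The same section says "The enrolment for each vaccine dose (adjuvanted or not) will be open in a staggered way". The 30 µg cohort opens once 10 µg enrolment is complete, and the 90 µg cohort once 30 µg enrolment is complete.

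**Models.** In SAP 3.3.5.2, for CD4+ frequency two weeks after the second vaccination, "The ANOVA model will include the doses" and the adjuvant as fixed effects, with a check of their interaction. For responders, dose, adjuvant "and interaction will be included in the logistic model". Neither model has a Day 0 term. A significant dose effect in the ANOVA leads to pairwise comparisons and an assessment of dose-response.

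**Baseline data.** CD4+ frequencies are endpoints "as determined by ICS at Months 0, 2, 6, 12" and Day 44 (SAP 2.2.2). Protocol Table 6 lists 180 subjects for ICS at Day 0. SAP 3.3.2 pools these values to set one responder cut-off, and SAP 3.3.5.1 tabulates Month 0 by group.

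**Caveat given.** The warning that opens SAP 3.3.5.2 covers multiplicity of endpoints and clinical relevance. It does not mention that dose is unrandomised or tied to order of enrolment.

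**The concern.** Because dose and enrolment cohort coincide, anything that differs between the cohorts enters the dose contrast: the subjects recruited, the handling of cells, the assay background. Randomisation protects the adjuvant contrast within each dose, but it does not protect the dose contrast. The SAP nevertheless tests dose formally and follows a significant result with dose-response statements.

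The subject's Day 0 frequency is the one measured quantity that could show, and partly absorb, a difference in background between cohorts. It could also reduce residual variance. It is already collected, and the models do not use it.

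**Working it through.** **1. The plan's own figure.** The only power statement for dose comparisons is Protocol Table 12: two groups of 50, Fisher's exact test, two-sided alpha 0.0167, 80% power. Full enumeration gives 0.786, 0.793, 0.803, 0.805, 0.806, 0.801, 0.800 and 0.788 for its eight rows, so the table reproduces. There is no such figure for the ANOVA.

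**2. Precision from a Day 0 covariate (linear model).** Inputs: 50 per adjuvanted group and alpha 0.0167 (Protocol 10.4). The correlation rho between Day 0 and Day 44 is not given and is assumed from 0.1 to 0.5.

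- Variance factor: 1 − rho².
- Equivalent group size: 50/(1 − rho²).
- Difference detectable with 80% power, in SD: (2.394 + 0.842) × √(2/50) × √(1 − rho²) = 0.647 × √(1 − rho²).
- Power is at the 0.647 SD difference that gives 80% without the covariate.

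| rho | Variance saved | Equivalent n | Detectable difference (SD) | Power |
|---|---|---|---|---|
| 0 | 0% | 50.0 | 0.647 | 80.0% |
| 0.1 | 1% | 50.5 | 0.644 | 80.5% |
| 0.2 | 4% | 52.1 | 0.634 | 81.8% |
| 0.3 | 9% | 54.9 | 0.617 | 84.1% |
| 0.5 | 25% | 66.7 | 0.560 | 91.0% |

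**3. What confounding could do.** Suppose there is no true dose effect, but Day 44 values drift linearly by a total of D SD from the first cohort to the last. D is an assumption; the documents give none. With 60 subjects per dose, the noncentrality of the dose F test (2 and 174 df, dose means weighted by cell size) is λ = 60 × Σ(μ − mean)² = 30D². At level 0.05:

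- D = 0.2: λ = 1.2, dose test significant in 14.9% of trials
- D = 0.3: λ = 2.7, 28.8%
- D = 0.5: λ = 7.5, 68.0%

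In the adjuvanted groups alone (50 per dose, λ = 25D²) the figures are 13.1%, 24.5% and 59.3%.

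**4. How much the covariate takes away.** With equal SDs the regression slope on Day 0 is rho. If a fraction k of the drift also shows at Day 0, the adjusted shift is D(1 − rho·k) and λ = 30D²(1 − rho·k)²/(1 − rho²). For D = 0.5, where the unadjusted figure is 68.0%:

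| rho | Shift remaining, k = 1 | False dose finding, k = 1 | False dose finding, k = 0 |
|---|---|---|---|
| 0.1 | 90% | 58.6% | 68.4% |
| 0.2 | 80% | 49.6% | 69.9% |
| 0.3 | 70% | 41.3% | 72.3% |
| 0.5 | 50% | 26.9% | 80.8% |

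Simulation of 3,000 trials per setting, at rho 0.1, 0.3 and 0.5, agrees to within 3 percentage points. When the drift is absent at Day 0 (k = 0), the covariate makes the false finding somewhat more likely, because it narrows the error around a contrast that is still biased.

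**5. Logistic model.** The rho² result belongs to the linear model. In logistic regression a covariate changes the odds ratio from marginal to conditional, so the table in step 2 does not apply to responder rates.

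**The case against.** The confounding comes from dose escalation for safety, and omitting a covariate did not create it. Enrolment is at one centre and short: "The enrollment period, i.e., the period between the study start and the last enrolled subject, is maximum 20 weeks". Subjects are seronegative with no earlier HIV vaccine (Protocol 4.2 and 4.3), so Day 0 ICS may be mostly background, rho low, and the gain a few percent. Month 0 results are tabulated by group, so a gross shift would be visible. The study is a first evaluation without a formal sample size, and SAP 2.5 reports that the analysis to Month 2 has been performed. All of this stands. It limits the benefit and fixes the label of any added analysis, but it does not supply the missing statement about sequential cohorts.

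Three stronger readings are tempting, and the documents support none of them.

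- A reader might infer that assay or calendar drift is being reported as a dose effect. No drift is documented. Cells are "further cryopreserved in liquid nitrogen until testing" (Protocol Appendix D), and how samples are batched is not stated; mixed runs would limit assay drift.
- A reader might infer that baseline adjustment would remove cohort differences. Step 4 shows that it removes about a fraction rho of a shared shift and none of a shift absent at Day 0.
- A reader might infer that all of a subject's samples should be tested in one run. That conflicts with the two-step analysis (Protocol 10.8), which needs Day 44 results before Month 12 samples exist.

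**Conclusion.** The point holds in limited form. Dose is confounded with enrolment cohort by design, SAP 3.3.5.2 does not say so, and the models leave out a baseline value planned for all 180 subjects. Using it in the ANOVA saves 1%, 4%, 9% or 25% of residual variance at assumed rho of 0.1, 0.2, 0.3 or 0.5; the lower values are the more plausible here. It lessens a shared background shift by about a fraction rho (equal SDs assumed) and leaves the rest of the confounding in place.

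The false-finding rates in steps 3 and 4 show sensitivity to assumed drifts and are not predictions. The adjuvant contrast, randomised within dose, is not biased by a drift that adds equally to both arms.

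**What to change.** 1. In SAP 3.3.5.2, state that dose contrasts are between non-randomised cohorts enrolled in sequence, so a dose difference cannot be fully separated from a cohort difference.
2. Add the subject's Day 0 frequency to the ANOVA as a covariate: same antigen (or F4co sum) and same cytokine definition as the outcome, on the log10 scale, with a stated rule for zeros. Where the Month 2 analysis is already done, label this a sensitivity analysis.
3. Treat a Day 0-adjusted logistic model as supportive only, because its odds ratio is conditional.
4. Compare Day 0 values across the three dose cohorts and report the comparison beside the dose tests.

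Cost: a few lines of SAP text, one degree of freedom and the rule for zeros. No new sample or assay is needed. Because SAP 3.3.4 does not replace missing values, a subject without a Day 0 result drops out of the adjusted model; report how many.
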